1. INTRODUCTION

When developing foods with potential health benefits, it is necessary to evaluate their acceptability and tolerability to determine whether the product will be consumed by the intended population. (Yang & Lee, 2018), In addition to ensuring that its consumption does not compromise the consumer's health, these tests allow the developer to make the necessary modifications to increase the likelihood of consumption.

The acceptability of a product can be studied through surveys or interviews and the way to apply these resources is through sensory tests oriented to the consumer, these tests allow to obtain information about the aspects that are liked and disliked about the product in question (Ramírez-Nava, 2012). To achieve this, sensory analysis is used, which is defined as the scientific discipline used to measure, identify and interpret food characteristics perceived by the senses of sight, smell, taste, touch and hearing (Lawless & Heymann, 2010). Among consumer-oriented tests, there are two main ones: preference tests and acceptance tests. In preference tests, consumers are asked to indicate which sample they prefer. While in acceptance tests, consumers are presented with the products and asked to indicate their level of liking them on a scale that can be 3, 5, 7, and 9 points (Sharif *et al.*, 2017). Acceptance tests are often used to compare two or more products or used on a single product to measure the level of liking.

Pregnancy is a stage that is marked by physiological changes related to hormones that modify sensory perception (Muluh *et al.*, 2024), mainly affecting taste (Choo & Dando, 2017) and smell (Haddad-Tóvolli *et al.*, 2023); However, this has been very little studied and most of the knowledge on the subject is empirical (Köhlble *et al.*, 2001), but it has now begun to be studied as the work conducted by Matsuda *et al.* (2024) who have suggested that oxytocin has an effect on the olfactory sensitivity of pregnant women, meanwhile Muluh *et al.* (2024) found moderate evidence of sensory changes during pregnancy, such as a reduction in the ability to identify odors and changes in the perception of the intensity of odors and hedonic responses to flavors.

The proposed beverage to be evaluated is made entirely from natural compounds, which in theory should not cause gastrointestinal intolerance effects, but to reaffirm this in the

acceptability test, a gastrointestinal tolerability questionnaire was included evaluating the presence or absence of symptoms such as nausea, regurgitation, vomiting, diarrhea, constipation and flatulence. (De Luis *et al.*, 2015).

In this work, a phase I pilot test was carried out, which consists of testing on a smaller scale the execution logistics planned for a higher-level project and thereby reducing the probability of errors in future studies (Díaz-Muñoz *et al.*, 2020). This work was approved by the Research Ethics Committee of the Biotic Products Development Center of the National Polytechnic Institute.

The study evaluated the gastrointestinal acceptability and tolerability of the proposed beverage developed to help control hypertensive disorders associated with pregnancy. Indicators such as blood pressure, blood markers of glucose, cholesterol, triglycerides and creatinine, and general urine test were also assessed. This trial was conducted on pregnant women, because this is the group to which the drink is directed and at this stage physiological changes occur that modify the sensory perception of food (Matsuda *et al.*, 2024), This is why it is important to conduct it in this group. This trial aims to lay the groundwork for defining the logistics used in a double-blind, randomized, controlled clinical trial in which the beverage will be given for a longer period of time. This is why it is important to know the acceptability of the beverage, in case it is necessary to make changes to the beverage that allow for increased consumption (Lawless & Heymann, 2010).

2. OBJECTIVES

2.1. General objective

Evaluate the acceptability, tolerability, blood pressure and biochemical indicators of a beverage with *Hibiscus sabdariffa* L. in pregnant women.

2.2. Specific objectives

- To evaluate the acceptability of the beverage by sensory analysis in a 4-week trial with a 7-point hedonic scale.
- Determine the tolerability of the beverage by the presence of gastrointestinal symptoms.
- Evaluate biochemical indicators, blood pressure and general urine test before and after the beverage consumption trial.

3. MATERIAL AND METHODS

A 4-week phase I pilot trial was conducted in 10 women in their second trimester of pregnancy, who consumed a daily dose of *H. sabdariffa* beverage. Acceptability and tolerability were assessed. Blood pressure, urinalysis, and blood biomarkers of glucose, cholesterol, triglycerides, and creatinine were also measured.

Figure 1 presents the experimental diagram of the beverage acceptability and tolerability test.

[figure not shown]

Figure 1. Experimental diagram of the acceptability and tolerability test of a beverage with *Hibiscus sabdariffa* L.

3.1. Ethical considerations

This research project complies with the International Ethical Guidelines for Research Related to Human Health, developed by the Council for International Organizations of Medical Sciences (CIOMS) in collaboration with the WHO.

All participants in this trial received dignified treatment and were not discriminated against under any circumstances based on their ethnic or national origin, social or economic status, religion, opinions, or marital status, in accordance with the Federal Law to Prevent and Eliminate Discrimination. Participants were never recruited against their will, nor did they suffer any form of disapproval or retaliation if they decided not to participate or withdrew from the study. It was emphasized that participation was completely voluntary and that they could refuse to participate or withdraw from the research at any time if they so desired.

The results obtained were used solely by the research team. The privacy of the participants, as well as the confidentiality of their personal information, was protected. All collected samples were identified by the participant's initials and a consecutive number, and only the researchers had access to their personal information. This information was kept safe with their file and will not be disclosed or published at any time. The results may be published for scientific purposes, but personal and identifying data of the participants will not be disclosed at any time. The results obtained were analyzed using Past software through pairwise analysis to determine statistical differences between the indicators measured before and after treatment with a significance level of $P < 0.05$. Descriptive statistics with means, standard deviations, and percentages were also applied to characterize the group.

The researchers of this protocol declare that there is no conflict of interest and that the objective is to generate knowledge that allows us to evaluate the effect of a beverage with *H. sabdariffa*, which can be used in the prevention and/or treatment of hypertensive disorders associated with pregnancy, as well as to determine its degree of acceptability and tolerability.

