3.3.2. Participants selection

Because this was a phase 1 pilot study, where participants were self-controlled, with marker measurements taken before starting to consume the beverage and at the end of the 4-week treatment period, the sample size was based on convenience. All women who met the inclusion criteria and did not meet the exclusion criteria were invited to participate. At least ten pregnant women were recruited through the consultation of PhD. [name], a specialist in obstetrics and gynecology and maternal-fetal medicine at the "MEDOMAI" Comprehensive Health Services Clinic located in Cuernavaca, Morelos, México.

Participants were selected according to the following criteria:

Inclusion criteria

- Pregnant women aged 18 to 35
- Those in their second trimester of pregnancy (14 – 28 gestation weeks)
- Blood pressure <140/90 mmHg

Exclusion criteria

- Multiple or high-risk pregnancy
- Having suffered from a hypertensive disorder in previous pregnancies

- Having chronic non-communicable diseases such as diabetes mellitus, cardiovascular disease, cancer, and chronic kidney disease
- Body Mass Index $\geq 32 \text{ kg/m}^2$

Elimination criteria

- Develop any pregnancy complications that prevent you from consuming the beverage and/or attending the measurements
- Deciding of your own volition to withdraw from the study

The patient records were reviewed to select patients who met the criteria for pregnancy weeks and age. They were contacted by telephone, where their medical history was taken to confirm that they met the remaining criteria. The procedures to be performed and how to prepare the beverage were explained in detail. In this conversation, the candidates were asked about their interest in participating and the date they should arrive to sign the informed consent form, receive the powdered doses to prepare the beverage along with its preparation instructions, and perform blood pressure measurements, biochemical indicators, and provide a urine sample.

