3.3.5. Blood pressure, urinalysis and biochemical markers

Blood pressure, urinalysis, and biochemical indicators of serum glucose, cholesterol, triglycerides, and creatinine were measured before the start of the trial and after the four weeks of consumption of the beverage were completed, to compare these parameters before and after treatment. The measurements and blood samples were taken by trained and experienced personnel. Blood pressure was measured using a noninvasive technique using the Korotkoff auscultation method.

Blood samples were obtained by puncture in the antecubital region of the participants' non-dominant arm, using sterile, disposable materials. Blood was placed in anticoagulant-free tubes for clinical chemistry, extracting 6 ml of blood. These tubes were kept refrigerated until the determinations were performed in the Biomarker Measurement Laboratory of the Biotic Product Development Center by personnel from the Department of Nutrition and Functional Foods, who are trained and experienced in sample collection and processing. Blood chemistry was measured using the Spinlab series 5-5312 semi-automated turbidimetry equipment for clinical chemistry.

The biological materials were used only for the aforementioned tests and were kept refrigerated until their disposal as Biologically Infectious Hazardous Waste (BIHW) in accordance with Mexican Official Standard NOM-087-SEMARNAT-SSA1-2002. The

results of the biochemical indicators were reported in writing to the participants, who received free medical and nutritional guidance, if necessary.

The general urine test was performed by the Jacobo Curiel external clinical analysis laboratory in Cuernavaca, Morelos. Participants submitted their samples to the "MEDOMAI" clinic on the indicated date, and the samples were then transferred to the external laboratory.

The researchers of this protocol declare that there is no conflict of interest and that the objective is to generate knowledge that allows us to evaluate the effect of a beverage with *H. sabdariffa*, which can be used in the prevention and/or treatment of hypertensive disorders associated with pregnancy, as well as to determine its degree of gastrointestinal acceptability and tolerability.

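### With about ten women and no main indicator, a P < 0.05 verdict on each before/after indicator supports neither an effect nor stability; report exploratory changes with confidence intervals (minor)

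*Protocol*

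**What the plan says.** The analysis rule sits in the Protocol, section 3.1 (Ethical considerations). The results are analysed "through pairwise analysis to determine statistical differences between the indicators measured before and after treatment with a significance level of" P < 0.05. The same paragraph adds means, standard deviations and percentages, but their stated role is to describe the sample.

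The indicators are listed in section 3.3.5: "Blood pressure, urinalysis, and biochemical indicators of serum glucose, cholesterol, triglycerides, and creatinine were measured before the start of the trial", and again after four weeks. None is singled out as the main one.

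On size, section 3 says "A 4-week phase I pilot trial was conducted in 10 women in their second trimester of pregnancy", while section 3.3.2 says "At least ten pregnant women were recruited" and that "the sample size was based on convenience". No effect size, SD or power target is given. Each woman is her own control, and there is no comparison group.

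**The concern.** The paragraph fixes what the before/after data are for: to decide, indicator by indicator, whether a difference exists at the 5% level. With several indicators and about ten pairs, that decision can mislead in two ways.

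- A P-value below 0.05 on one of several indicators is easily read as an effect of the beverage. Sections 3.1 and 3.3.5 invite that reading, because they state the purpose as learning about the beverage's effect, with hypertensive disorders of pregnancy in view.
- A P-value above 0.05 on, say, glucose or creatinine is easily read as showing that the indicator stayed stable.

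The quantity that would inform a reader in either case is the size of the change and its precision. The plan does not make that the basis for its conclusions. The SD of the change also cannot be recovered from separate before and after SDs unless the before/after correlation r is known, because SD²(change) = SD²(before) + SD²(after) − 2·r·SD(before)·SD(after).

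**Working it through.** The Protocol states no power and no calculated sample size, so there is no figure to reproduce. The check asks what the stated rule delivers.

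**Inputs**

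- Level: 0.05 per comparison (section 3.1). Two-sided is assumed, since the aim is stated as differences without a direction.
- Test: paired comparison (section 3.1). The type is not named, so a paired t-test is used, with the signed-rank test as a check.
- Pairs: n = 10 (section 3). Section 3.3.2 allows more women, and withdrawals would leave fewer pairs.
- Number of indicators: k = 6, made up of systolic pressure, diastolic pressure, glucose, cholesterol, triglycerides and creatinine. This count is an assumption. The Protocol gives no number, k is 5 if blood pressure counts once, and it rises if urinalysis items are tested.
- SD: none is given. Changes are therefore expressed in SDs of the within-woman change, which is also an assumption.

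**Chance of at least one P < 0.05 when nothing truly changes**

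For independent tests this is 1 − 0.95^k:

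- k = 5: 1 − 0.95^5 = 22.6%
- k = 6: 1 − 0.95^6 = 26.5%
- k = 7: 1 − 0.95^7 = 30.2%

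Simulation with k = 6, n = 10 and equal correlation between the changes gives 24.8% at 0.3, 21.8% at 0.5 and 17.8% at 0.7. At an extreme correlation of 0.9 it is 11.6%. If only systolic and diastolic pressure correlate (0.7), it is 25.7%.

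**Chance of missing a true change**

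Power comes from the noncentral t distribution with n − 1 = 9 degrees of freedom, noncentrality d·√n and critical value 2.262. For d = 0.5 the noncentrality is 0.5 × √10 = 1.58.

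| True change (SDs of the change) | Power, n = 10 | Missed |
|---|---|---|
| 0.5 | 29.3% | 70.7% |
| 0.8 | 61.6% | 38.4% |
| 1.0 | 80.3% | 19.7% |

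For d = 0.5 the miss rate is 76.8% with 8 pairs and 64.7% with 12. The signed-rank test with 10 pairs misses about 72%, so the choice of test hardly matters.

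**Dependence on the SD scale**

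If half an SD refers to the raw values, then d = 0.5/√(2(1 − r)), where r is the before/after correlation. The miss rate with 10 pairs is then 83% at r = 0, 71% at r = 0.5, 55% at r = 0.7 and 12% at r = 0.9. The 71% figure therefore belongs to the within-woman scale, or to r = 0.5.

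**Precision**

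The half-width of a 95% CI for the mean change is 2.262/√10 = 0.715, or about 0.72 SDs of the change.

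**The case against.** The strongest reply is that the Protocol makes none of the claims these figures would refute. It states no power, explains its size as convenience in a phase I pilot, and nowhere says that one significant indicator will establish an effect or that a non-significant one will establish stability. For any single indicator the error rate is the nominal 5%. A multiplicity rule or a named main indicator might also sit in a statistical analysis plan that is not shown. All of this stands. It means that no figure is wrong and that a missing adjustment is not in itself a fault. It does not rescue the rule that section 3.1 does fix, which uses a 5% threshold to determine differences.

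A reader might infer three stronger points that the documents do not support.

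- **That the later randomized trial depends on these changes.** The Introduction says the pilot prepares the logistics of that trial and stresses acceptability. It does not say that biomarker changes will size it.
- **That the remedy is to adjust for multiplicity.** At 0.05/6 = 0.0083, which is the Bonferroni level and the first step of Holm, power for 0.5 SDs of the change falls from 29% to about 9%. One weakness would be exchanged for a larger one. Nor could adjustment attribute a change to the beverage in a single group followed through four weeks of pregnancy.
- **That the pilot is too small.** Reaching 80% power at 0.5 SDs of the change would take 34 pairs, but nothing in the Protocol commits it to that target.

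The statistical paragraph is also written in the past tense. A change to it now would act as a reporting rule rather than as prespecification.

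**Conclusion.** The point holds as a minor one. Under the stated rule, and with no true change, at least one of six indicators reaches P < 0.05 with a chance of roughly 18% to 26.5%, for correlations from 0.7 down to independence. A true change of 0.5 SDs of the within-woman change is missed about 71% of the time with ten pairs. The verdict is therefore weak evidence in both directions.

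These sizes rest on the count of six, two-sided paired tests, ten complete pairs and the within-woman SD scale. It would be too strong to say without those conditions that one study in four gives a false positive, or that any half-SD change is missed 71% of the time. The documents fix neither the number of tests nor their correlation, and they give no SD.

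**What to change.** In the statistical paragraph of section 3.1, replace the significance verdict with estimation. For each continuous indicator, report the mean within-woman change, the SD of the change, its 95% CI and the number of pairs used. Label these results exploratory. Add one sentence saying that neither an effect of the beverage nor stability of an indicator will be concluded from a P-value.

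The cost is one paragraph of wording and six confidence intervals, from paired data that the study already collects. The downside is that no indicator can be headlined as significant, and with ten pairs the intervals will be visibly wide, at about ±0.72 SDs of the change.

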3.2. Materials

The proposed beverage was made with *H. sabdariffa* calyces from the Temixco cultivar in Morelos, and was given to participants as a powder for beverage preparation. The powder contained 5.7 g of powdered *H. sabdariffa* calyces and 5 g of standard sugar.

3.3. Methods

3.3.1. Microbiological analysis of *Hibiscus sabdariffa* L. calyces

Prior to the acceptability and tolerability test of the beverage, a microbiological analysis of the powdered calyces of *H. sabdariffa* was performed, measuring mesophilic counts, total coliforms, molds, yeasts, *Escherichia coli* and *Salmonella* spp. to ensure the safe consumption of the hibiscus. All indicators were within permissible values according to Mexican standards.

3.3.2. Participants selection

Because this was a phase 1 pilot study, where participants were self-controlled, with marker measurements taken before starting to consume the beverage and at the end of the 4-week treatment period, the sample size was based on convenience. All women who met the inclusion criteria and did not meet the exclusion criteria were invited to participate. At least ten pregnant women were recruited through the consultation of PhD. [name], a specialist in obstetrics and gynecology and maternal-fetal medicine at the "MEDOMAI" Comprehensive Health Services Clinic located in Cuernavaca, Morelos, México.

Participants were selected according to the following criteria:

Inclusion criteria

- Pregnant women aged 18 to 35
- Those in their second trimester of pregnancy (14 – 28 gestation weeks)
- Blood pressure <140/90 mmHg

Exclusion criteria

- Multiple or high-risk pregnancy
- Having suffered from a hypertensive disorder in previous pregnancies

- Having chronic non-communicable diseases such as diabetes mellitus, cardiovascular disease, cancer, and chronic kidney disease
- Body Mass Index $\geq 32 \text{ kg/m}^2$

Elimination criteria

- Develop any pregnancy complications that prevent you from consuming the beverage and/or attending the measurements
- Deciding of your own volition to withdraw from the study

The patient records were reviewed to select patients who met the criteria for pregnancy weeks and age. They were contacted by telephone, where their medical history was taken to confirm that they met the remaining criteria. The procedures to be performed and how to prepare the beverage were explained in detail. In this conversation, the candidates were asked about their interest in participating and the date they should arrive to sign the informed consent form, receive the powdered doses to prepare the beverage along with its preparation instructions, and perform blood pressure measurements, biochemical indicators, and provide a urine sample.

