3.3.3. Acceptability and beverage consumption adherence

Beverage acceptance was assessed through a sensory analysis once a week for 4 weeks using a 7-point hedonic scale, considering the characteristics of color, odor, flavor, mouthfeel, aftertaste, and overall appearance. The scoring system was as follows: 1 = I dislike it a lot, 2 = I dislike it moderately, 3 = I dislike it a little, 4 = I neither like it nor dislike it, 5 = I like it a little, 6 = I like it moderately, and 7 = I like it a lot. To conduct this assessment, participants were sent a Google Form via WhatsApp. This form also included a section to indicate any other sensations they perceived when consuming the beverage, as well as their percentage of daily consumption of the beverage, and thus assess attachment.

Beverage acceptance is assessed using the hedonic scale, and the score is evaluated whether the score is maintained over the duration of the trial. The feedback provided by participants allows adjustments to improve beverage acceptance, if necessary.

3.3.4. Gastrointestinal tolerability due to consumption of the beverage.

Once a week for the 4 weeks of the trial, participants completed a gastrointestinal tolerability assessment form as proposed by De Luis *et al.* (2015), where participants indicated the presence or absence of gastrointestinal symptoms such as nausea, regurgitation, vomiting, constipation, diarrhea, flatulence, and abdominal pain. These symptoms were assessed using 5 points where: 0=absent symptom, 1=symptom present but not bothersome, 2=annoying symptom but does not interfere with daily activities or sleep, 3=a symptom present and bothersome but does interfere with daily activities and sleep, and 4=a symptom present that requires medical attention.

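### Voluntary withdrawal is listed as an elimination criterion among the selection rules; read as removal from the study group, it drops women who stop over dislike or symptoms from the acceptability and tolerability results

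*Protocol*

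**What the plan says.** Section 3.3.2 of the protocol introduces its criteria with "Participants were selected according to the following criteria" and then gives three lists: inclusion, exclusion and elimination. The elimination list has two items:

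- "Develop any pregnancy complications that prevent you from consuming the beverage and/or attending the measurements"
- "Deciding of your own volition to withdraw from the study"

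Neither item makes an exception for women who stop because of the drink itself. The protocol does not define elimination. It does not say whether an eliminated woman's weekly forms are kept or set aside, or whether she is replaced.

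Two other statements bear on the meaning. The invitation sentence in the same section uses only the first two lists: "All women who met the inclusion criteria and did not meet the exclusion criteria were invited to participate". Section 3.1 gives every participant the right to leave: "they could refuse to participate or withdraw from the research at any time if they so desired".

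Section 2.2 makes acceptability (7-point hedonic scale) and tolerability (gastrointestinal symptoms) the first two specific objectives. Section 3.3.3 collects the hedonic scores and section 3.3.4 the symptom grades, both once a week for four weeks.

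**The concern.** Disliking a drink, or feeling unwell after it, is a plausible reason to stop taking it. In an acceptability and tolerability study, a withdrawal for either reason is part of the result. If withdrawal also takes the woman out of the group that is summarised, the least favourable experiences are the ones most likely to go uncounted, and both results look better than they were.

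Section 1 says the trial is to prepare the logistics of a longer double-blind randomised trial. How many women stop, and why, is an input to planning that trial, and it is lost if leavers are treated as never having belonged to the group.

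**Working it through.** **Step 1. What elimination can mean.** Two readings fit the text.

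| | Ends participation only | Removes from the study group |
|---|---|---|
| Support | The invitation sentence uses only the inclusion and exclusion lists; section 3.1 already grants withdrawal; both events occur after joining | The list stands under the sentence saying participants were selected by these criteria; both events end participation anyway, so a list that does no more than that adds nothing |
| Weekly forms before leaving | Kept | Could be set aside |
| Effect on acceptability and tolerability | None from this rule | Bias in favour of the drink if women left over dislike or symptoms |

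The protocol does not choose between them.

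**Step 2. Is there a figure to reproduce?** No. The sample size is stated to be one of convenience. The document gives no withdrawal rate, number of leavers, hedonic mean or symptom frequency, so the actual bias cannot be computed. What follows is illustration on assumed values.

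**Step 3. Acceptability, illustration.** Assume ten starters, of whom k leave and are removed; stayers score 6 and leavers 2 in week 1.

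Mean over all starters = [6(10 − k) + 2k] / 10. Mean reported after removal = 6.0. Overstatement = 0.4k.

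- k = 0: 60/10 = 6.0; no overstatement
- k = 1: (54 + 2)/10 = 5.6; overstatement 0.4
- k = 2: (48 + 4)/10 = 5.2; overstatement 0.8
- k = 3: (42 + 6)/10 = 4.8; overstatement 1.2

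The direction depends on why women leave. A leaver who also scored 6 causes no shift. One leaver who scored 7 gives (54 + 7)/10 = 6.1, so the reported 6.0 would be 0.1 too low.

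**Step 4. Tolerability, illustration.** Assume that no stayer is intolerant and that every leaver is. The protocol grades several symptoms from 0 to 4 and defines no yes/no intolerance outcome, so this classification is also an assumption. Exact (Clopper-Pearson) 95% intervals:

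| Leavers | After removal | All ten starters |
|---|---|---|
| 0 | 0/10 (0 to 30.8%) | 0/10 (0 to 30.8%) |
| 1 | 0/9 (0 to 33.6%) | 1/10 (0.3 to 44.5%) |
| 2 | 0/8 (0 to 36.9%) | 2/10 (2.5 to 55.6%) |
| 3 | 0/7 (0 to 41.0%) | 3/10 (6.7 to 65.2%) |

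Each such leaver moves the point estimate by 10 percentage points. The intervals overlap throughout.

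**The case against.** The strongest reply is that elimination simply means the end of participation. The second item does little more than restate the right to withdraw in section 3.1, and neither event can occur before enrolment, so the list cannot literally select anyone. The ethics committee's annex names inclusion, exclusion and elimination criteria together, which suggests a conventional heading and not an analysis rule. Analysis sets and missing data are commonly left to a SAP, which may exist. The weekly form also records percentage consumption and free comments, so dislike could show before a woman leaves. Finally, the illustrations rest on invented leavers and scores.

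Much of this stands. A reader might infer that leavers' data were in fact discarded; the protocol does not say so. Nor does it report that anyone left, so no actual bias is shown. Two further inferences also fail:

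- **A conflict over the number of women.** "A 4-week phase I pilot trial was conducted in 10 women in their second trimester of pregnancy" is consistent with "At least ten pregnant women were recruited", since ten satisfies at least ten. Whether the ten are starters or completers is a matter for the report.
- **A flaw in how acceptance is judged.** Section 3.3.3 says "the score is evaluated whether the score is maintained over the duration of the trial", but not that this is done on raw weekly means. The method is a detail that a SAP may hold.

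What does not stand is that the point is only missing detail. This protocol itself puts withdrawal among its selection criteria, and a SAP would still have to interpret that. The consumption record and comments help only if the forms carrying them are kept.

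**Conclusion.** The point holds as a conditional one. The protocol places two post-enrolment events among the criteria by which participants were selected. If that is applied as removal from the study group, women who stop over dislike or symptoms leave the two results that their stopping most concerns, and those results are biased in favour of the drink. Withdrawals for unrelated reasons need not bias anything.

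The size is unknown. It is nil if nobody left for such reasons. On the assumed values above, one to three leavers among ten starters overstate the hedonic mean by 0.4 to 1.2 points and understate intolerance by 10 to 30 percentage points. These figures show only that single women carry weight in a group of ten; they do not estimate what happened. The wording should be corrected because it bears on two of the three specific objectives and the correction is easy.

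**What to change.** State that the elimination criteria end a woman's participation and do not remove her from analysis. Analyse acceptability and tolerability in all women who took at least one dose, using every weekly form returned, unless a woman withdrew consent to the use of her data. Report the number who left and their reasons, where known, beside the hedonic and symptom results.

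As the protocol describes a trial already run, apply this to its report and carry the wording into the later randomised trial. If nobody left, one sentence in the report settles the matter.

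The cost is wording and reporting only, with no extra women or procedures, and the rules on when a woman stops are untouched. The results may look slightly less favourable, and some reasons for leaving may be unknown.
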